#### Abstract

**Introduction:** Helicobacter pylori (H. pylori) infection remains a major public health problem, with an estimated prevalence of over 50% worldwide and 60-86% for Portugal. H. pylori is associated with significant morbidity and mortality from peptic ulcerative disease to gastric cancer, whose eradication therapy has proven to be effective in preventing these complications. Factors involved in the development of these conditions include H. pylori virulence, host genetic factors and gut microbiota. Given the increasing pattern of antibiotic resistance evidenced by this bacterium and the scarcity of available antibiotic therapy, both in Portugal and worldwide, there is not enough evidence on the best eradication strategy. Regarding the uncertainties about the potential negative impact of indiscriminate use of eradication therapy on gut microbiota, either by proton pump inhibitors or by antibiotics per se, there is an overriding need for evidence about the real impact of this therapy on gut flora and possible clinical consequences in immunological, metabolic, nutritional and oncological terms. **Objectives:** Comparative evaluation of the efficacy of the different quadruple therapy regimens recommended for the H. pylori eradication. Comparative evaluation of the safety profile in terms of clinical, immunological and gut microbiota impact of the different therapies for the H. pylori eradication. **Methods:** Prospective longitudinal multicentre study of total of patients with gastric infection by H. pylori, diagnosed by C-urea breath test or histological analysis of gastric biopsies and clinical indication for its eradication, referred to the different participating Portuguese hospital units and a blind randomized controlled clinical trial of the efficacy and safety of the different quadruple therapy regimes recommended for the H. pylori eradication. This study will be carried out in 4 phases: Phase 1 - Recruitment and randomization of patients by the different quadruple eradication schemes with and without bismuth (5 parallel arms); Phase 2 - H. pylori eradication with evaluation of the efficacy and safety rates at 1 month and the absence of reinfection at 12 months after treatment and collection of stool samples before and after the eradication therapy for evaluation of changes in gut microbiota; Phase 3 - Analysis of richness, diversity and uniformity of gut microbiota by DNA sequencing using the hypervariable region of the ribosomal 16S bacteria gene as a taxonomic identification marker and their clinical impact on immunology, metabolism and nutrition at 12 months after the H. pylori eradication therapy; and Phase 4 - Analysis of immunological changes through the study of cell populations by flow cytometry (CD4+, CD8+, B-cell, T-cell, natural killer cells, cells ratio) and cytokines, chemokines and growth factors by xMAP/Luminex before and 12 months after the H. pylori eradication therapy. **Expected results, impact and scientific outputs:** Given the high rate of triple therapy inefficacy, high antibiotic resistance and the scarcity and controversy of existing literature on quadruple regimens, there may be relevant differences in the approved quadruple regimens for the H. pylori eradication, being necessary to define which is the most effective and safe in Portugal, decreasing the rate of ineffectiveness and exposure to multiple antibiotics. The homeostasis of gut microbiota is significantly changed after H. pylori eradication and this modification may be

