## Literature Review

*Helicobacter pylori* (*H. pylori*) infection remains a major public health problem, affecting over 50% of the worldwide population and 60-86.4% of the Portuguese population. This bacterium is responsible for chronic active gastritis, likely to develop into peptic ulcerative disease, atrophic gastritis, gastric adenocarcinoma and mucosal-associated lymphoid tissue lymphoma. Factors involved in the development of these conditions include bacterial virulence, host genetic factors and gut microbiota. *H. pylori* eradication therapy has been shown to be effective in preventing the development or recurrence of these complications. However, the increase in primary and secondary resistance of this bacterium to most antibiotics has reduced the efficacy of this therapeutic strategy. As in the rest of Europe, overall resistance to multiple antibiotics is high in Portugal, with a prevalence of 42-50% for clarithromycin, 25-34.4% for metronidazole, 18-33.9% for levofloxacin, 0.2-0.6% for tetracycline, 0.1-0.6% for amoxicillin and 20% for clarithromycin and metronidazole. Taking into account the pattern of *H. pylori* antibiotic resistance in Portugal and the selection flowchart proposed by [GrLeWu14], the currently recommended therapeutic regimens include quadruple therapies: sequential, hybrid, concomitant with bismuth and concomitant bismuth-free. However, some studies including quadruple schemes have shown unsatisfactory results, not exceeding 90% considered as the minimum efficacy rate. Given the high rate of resistance of *H. pylori* to nitroimidazoles registered in Portugal, it would be worth considering therapeutic optimization with metronidazole 500mg tid and not only bid. Thus, at present, there are no solid data that allow us to state the best therapeutic option in this country, being essential to conduct a randomized study to definitively resolve this uncertainty. Animal and human studies have shown that *H. pylori* results in changes in gut microbiota. Human gut microbiota represents a dynamic and complex ecosystem in close linking with the immune system, regulating gastrointestinal homeostasis. It is composed mostly of Gram-negative anaerobic bacilli, mainly Bacteroidetes and Fusobacteria. Gut dysbiosis has been associated with immune, metabolic, nutritional and oncological changes, such as the development of several gastrointestinal and systemic conditions such as inflammatory bowel disease, obesity, diabetes mellitus, metabolic syndrome, dyslipidemia, asthma and allergies. However, the interactions between *H. pylori*, gut microbiota and host pathophysiology are still far from being understood. Similarly, there are also uncertainties regarding the potential negative impact of indiscriminate use of *H. pylori* eradication therapy on the gut microbiota, mediated by either proton pump inhibitors or antibiotherapy. In some recent studies, eradication of *H. pylori* has been associated with a decrease in butyrate-producing bacteria (such as *Faecalibacterium prausnitzii*), Proteobacteria, Actinobacteria and Firmicutes, and an increase in several potentially harmful bacteria such as Bacteroidetes and the Bacteroidetes:Firmicutes ratio. These changes persist until 12-18 months after *H. pylori* eradication therapy, although in one study changes in gut microbiota

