### **B. Objectives**

- To determine and compare the efficacy of the different therapeutic regimens recommended as *H. pylori* eradication therapy;
- Comparative evaluation of the safety profile in terms of clinical, immunological and gut microbiota impact of the different recommended therapies for the *H. pylori* eradication:
- To evaluate the changes in gut microbiota after the *H. pylori* eradication therapy;
- Compare the changes in gut microbiota induced by the different therapeutic regimens for *H. pylori* eradication and evaluate their clinical implications on immunology, nutrition and metabolism;
- To evaluate the immunological changes after the *H. pylori* eradication therapy;
- Compare the immunological changes induced by the different therapeutic regimens for *H. pylori* eradication and evaluate their clinical implications.

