## **D. Methodology and Phases of project development**

### **D.1 Type of study**

Prospective longitudinal multicentre study and a blind randomized controlled trial involving several hospital units in Portugal. Regarding the evaluation of gut microbiota and immunological changes, the study will be blinded, since the researchers responsible for sequencing and immunological analysis will not know the therapeutic scheme applied. The trial will be registered on the <https://clinicaltrials.gov> platform.

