#### **Phase 2.** Eradication of H. pylori and collection of stool and blood samples

Stool samples shall be collected from patients and analyzed on 3 occasions: before (baseline), after stopping treatment (Day 10 or 14) and 1 month after treatment (Day 40 or 44). Blood samples will be collected and analyzed on 2 occasions: before (baseline) and 12 months after treatment. Efficacy and safety rates of H. pylori eradication will be determined for each therapeutic regimen. Carbon 13-labeled urea breath test or upper gastrointestinal endoscopy with biopsies will be performed at 1 month (D40 or D44) and 12 months after treatment. The clinical data, adherence and therapy-related adverse events will be recorded at baseline and during follow-up at 1 and 12 months post-eradication.

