#### **Phase 3.** Analysis of gut microbiota changes by DNA sequencing after H. pylori eradication therapy and their clinical impact on immunology, metabolism and nutrition

The impact of H. pylori eradication therapy on gut microbiota will be studied by next generation genome sequencing techniques. A comparative analysis will be performed for each therapeutic regimen used. Microbiota changes found will be compared with clinical and analytical data in order to establish their impact on immunology, metabolism and nutrition status at 1 and 12 months post-eradication. Phase 4. Analysis of immunological changes of cell populations, cytokines, chemokines and growth factors after H. pylori eradication therapy and their clinical impact. The impact of H. pylori eradication therapy on humoral and cellular immunity will be studied by flow cytometry and xAMP/Luminex. A comparative analysis will be performed for each therapeutic regimen used. Immunological changes found will be compared with clinical and analytical data in order to establish their clinical impact at 12 months post-eradication.

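### Adverse events are to be recorded as therapy-related, so the clinical adverse-event comparison between regimens may depend on a causality judgement by staff not described as masked

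*Combined protocol and SAP*

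**What the plan says.** The only rule for collecting adverse events is one sentence in section D.3, Phase 2. It names clinical data as its first item and says of the other two: "adherence and therapy-related adverse events will be recorded at baseline and during follow-up at 1 and 12 months post-eradication". The same paragraph promises that "Efficacy and safety rates of H. pylori eradication will be determined for each therapeutic regimen".

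Safety is a comparative aim. Section B lists "Comparative evaluation of the safety profile in terms of clinical, immunological and gut microbiota impact" across the recommended therapies, and the Abstract gives it as one of two objectives.

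On masking, the Abstract calls the study "a blind randomized controlled clinical trial of the efficacy and safety of the different quadruple therapy regimes" without saying who is blind. Section D.1 gives the only detail: "the researchers responsible for sequencing and immunological analysis will not know the therapeutic scheme applied".

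Late effects have a separate route. Phase 3 states: "Microbiota changes found will be compared with clinical and analytical data in order to establish their impact on immunology, metabolism and nutrition status". The time points for this are months 1 and 12. Phase 4 does the same for immunological changes at 12 months. The content of the clinical data is not defined in any section.

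**The concern.** In the Phase 2 sentence, relatedness describes which events are recorded. It is not a label added to events already on file. If sites follow the sentence as written, someone must decide that the regimen caused an event before it enters the adverse-event record. The plan names no assessor and gives no causality criteria, and the only people it describes as masked work in the laboratories.

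A recorded rate then has two parts: how often events occur, and how often staff attribute them to treatment. Randomisation balances the first across arms. It does not balance the second if the person judging knows the regimen and expects one to be worse tolerated than another. An event left out of the adverse-event record at that point can be recovered only if some other record happens to hold it.

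The rule also fits poorly with what the study wants to learn. Section A supposes that eradication therapy may have immunological, metabolic and nutritional consequences. The Literature Review links dysbiosis with "inflammatory bowel disease, obesity, diabetes mellitus, metabolic syndrome, dyslipidemia, asthma and allergies" and says that the interactions are far from understood. Asking a site to settle causation before reporting such an event as an adverse event assumes an answer that the trial does not yet have.

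**Working it through.** **Reading the sections together**

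1. *Capture.* D.3, Phase 2 names therapy-related adverse events. No other section mentions events regardless of cause, treatment-emergent events, grading, seriousness or a causality assessor.
2. *Masking.* D.1 covers the sequencing and immunology researchers. The Abstract's general label adds no role. Clinical staff are therefore not described as masked, although the plan does not say outright that they are unmasked.
3. *Baseline.* Before the first dose no event can be related to therapy, so a baseline entry of therapy-related events has no content. The same sentence also records clinical data at baseline. These could hold pre-treatment symptoms, but the plan does not say that they do.
4. *Late effects.* Phases 3 and 4 use clinical and analytical data, and Phase 2 takes blood at baseline and 12 months. Neither route requires attribution to therapy.

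**Number per arm**

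The plan's figure reproduces from section D.3: n = z²p(1−p)/e² with z = 1.96, p = 0.864 and e = 0.10 gives 3.8415 × 0.864 × 0.136 / 0.01 = 45.14. This rounds up to 46, and 46 × 5 = 230. It is used below only as the arm size.

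**Illustration (event and attribution rates are assumptions; the documents give none)**

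Recorded rate = true rate × probability of attribution.

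- True rate 30% in both arms, attribution 90% against 60%: 0.30 × 0.90 = 27% and 0.30 × 0.60 = 18%. The gap is 9 points (12.4 against 8.3 of 46) with no true difference.
- True rate 30%, attribution 80% against 70%: 24% and 21%, a gap of 3 points.

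The chance of declaring a false difference between one pair of arms follows from a two-sided 0.05 comparison of two proportions (sidedness assumed; normal approximation). With recorded rates p₁ and p₂ and mean p̄, SE₀ = √[2p̄(1−p̄)/46] and SE₁ = √[(p₁(1−p₁) + p₂(1−p₂))/46]. The probability is Φ[(|p₁−p₂| − 1.96·SE₀)/SE₁] + Φ[(−|p₁−p₂| − 1.96·SE₀)/SE₁].

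For 27% against 18%, SE₀ = 0.0871 and SE₁ = 0.0866, so the probability is Φ(−0.93) + Φ(−3.01) ≈ 0.18.

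| Attribution in the two arms | True rate 30% | True rate 50% | True rate 70% |
|---|---|---|---|
| 80% and 80% | 5% | 5% | 5% |
| 80% and 70% | 6% | 8% | 10% |
| 90% and 70% | 10% | 16% | 27% |
| 90% and 60% | 18% | 32% | 52% |
| 90% and 50% | 29% | 52% | 78% |

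Equal attribution does not inflate false positives, but it costs power. For true rates of 60% against 30%, power is about 84% if all events are recorded. It falls to 58%, 40% or 24% if 70%, 50% or 30% of events are attributed in both arms.

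**The case against.** The strongest reply is that one summary sentence is being read as an exclusion rule. It does not say that only related events are kept, sets no relatedness test and names no assessor. It applies a single visit list to three items, and adherence cannot be recorded before treatment either, so it may be loose shorthand. Clinical data appear in the same sentence at all three visits.

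Much of this stands, and it rules out several stronger readings that a reader might infer:

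- *That an event judged unrelated is never written down.* The documents do not show this. It may be lost from the adverse-event record, but the undefined clinical data might hold it.
- *That pre-treatment symptoms cannot be separated from new ones.* Separation is not assured, but it is not excluded.
- *That late systemic harms would be recorded as zero in every arm whatever the truth.* At most this could happen in the adverse-event record, and only if no site attributed them to therapy. Phases 3 and 4 look at late effects without an attribution filter, and the Literature Review's disease list is background, not a list of endpoints.
- *That the whole safety objective is exposed.* Two of its three components, immunology and microbiota, are laboratory measures analysed by masked researchers.

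It is also fair to say that nothing in the documents shows that staff hold different expectations by regimen, and that 12 against 8 events of 46 in a single trial would give z ≈ 1.0, p ≈ 0.31.

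Relevant detail might lie in text that was not supplied. Section D.4 points to a Tasks section, and reference 28, a proposed side-effect scoring system for *H. pylori* treatment studies, is not cited in the supplied text. But D.4 cites the Tasks section for efficacy, microbiota and immunological analyses, not for safety. Neither item shows that all events are recorded.

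The reply does not remove the point. The one rule that the plan states makes relatedness the condition for recording an adverse event, and the mention of undefined clinical data gives no assurance that other events are captured.

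**Conclusion.** The concern holds for the clinical adverse-event comparison between regimens, and no further. As written, the rates in that comparison may depend on a causality judgement by staff not described as masked. Events judged unrelated can drop out of the adverse-event record, and its baseline entry offers no reference for change.

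The size is unknown. Under the assumed inputs, a spurious gap between two arms runs from 3 to 9 points at a true rate of 30% with attribution of 80% against 70% or 90% against 60%. The chance of a false difference ranges from 5% with equal attribution to 78% in the most extreme case tabulated. These figures show how the mechanism works and do not forecast what this trial would find.

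The conclusion rests on two inferences: that sites would apply the Phase 2 sentence as written, and that the staff judging relatedness may know the regimen. A reader might go further and conclude that the safety results will be biased or that late harms will be missed. The documents support neither. The plan should still be changed, because the safety comparison is one of its two stated objectives and the correction is small.

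**What to change.** In section D.3, Phase 2, replace the reference to therapy-related adverse events with: all adverse events regardless of presumed cause, with onset date, severity and seriousness, and relatedness recorded as a separate field. At baseline, record the same symptom list and relevant diagnoses that will be asked about at follow-up. In section D.4, state that arms are compared first on all events that are new or worse than at baseline, with the therapy-related subset reported second.

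The cost is a change of wording and a few more form entries at visits already planned. Headline adverse-event rates will look higher. The sample size does not change.

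The change removes the causality filter. It does not remove all bias, since staff who know the regimen could still elicit or grade events differently. Having relatedness judged by assessors masked to regimen would help with that field but not with elicitation.

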#### **D.4 Statistical Analysis**

Using the Statistical Package for the Social Sciences (SPSS) version 22.0 (IL, USA). The level of statistical significance will be for a p-value  $< 0.05$ . The normality of data distribution will be evaluated by Kolmogorov-Smirnov or Shapiro-Wilk tests. Continuous variables will be expressed as mean and standard deviation or median and interquartile range and categorical variables as frequency and percentage. The comparison of continuous variables will be made using the Kruskal-Wallis test or Anova test and categorical variables using the Chi-squared test. For the comparison of paired data the Wilcoxon test or Friedman test and the t-Student or Anova test will be used. Further statistical analysis of H. pylori eradication efficacy, gut microbiota and immunological changes is described in Tasks section. The genome sequences will be grouped in OTU according to their similarity. The alpha taxonomic richness and diversity of fecal samples will be expressed in observed species, Sobs index and Shannon index. The composition of fecal

microbiota will be expressed in rarefaction curves and the comparison of the differences in OTU richness with the t-Welch test. Immunological findings will be expressed by radar charts and representative FACS dot-plots. Additional statistical analyses will be defined throughout the study.

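### The stated schedule has no adherence or adverse-event record between baseline and Day 40/44, although a stool sample is already collected at the end of treatment (Day 10/14)

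*Combined protocol and SAP*

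**What the plan says.** All the timing is in D.3, Phase 2.

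- Stool is collected at baseline, then "after stopping treatment (Day 10 or 14) and 1 month after treatment (Day 40 or 44").
- The breath test, or endoscopy with biopsies, "will be performed at 1 month (D40 or D44) and 12 months after treatment".
- For clinical data, adherence and tolerability, the plan says that "adherence and therapy-related adverse events will be recorded at baseline and during follow-up at 1 and 12 months post-eradication".

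The Abstract agrees on the timing of safety: it describes "evaluation of the efficacy and safety rates at 1 month and the absence of reinfection at 12 months after treatment".

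The safety data have a stated use. Phase 2 says that "Efficacy and safety rates of H. pylori eradication will be determined for each therapeutic regimen", and section B lists "Comparative evaluation of the safety profile in terms of clinical, immunological and gut microbiota impact of the different recommended therapies" among the objectives. The hypothesis in section A also refers to higher safety of one regimen over the others.

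The public document does not say how adherence or adverse events are obtained: no diary, tablet count, telephone contact or side-effect form appears in it.

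**The concern.** Events caused by a 10- or 14-day course occur mostly during that course. Of the three listed recording times, baseline comes too early to capture them and 12 months is remote, so the 1-month record carries the on-treatment information. If nothing is written down before then, what reaches the database depends on what the patient still reports a month after the last dose. Mild events are the likeliest to be lost.

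At stake is the clinical part of the comparative safety objective. If events are under-reported to the same degree in every arm, each regimen's rate is too low and the absolute differences between regimens shrink. Adherence has a similar problem. It helps in reading both the eradication rate and the end-of-treatment microbiota sample, yet that sample has no adherence record from its own time point. Once a patient has passed the end of treatment, a record made at that time cannot be recreated.

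**Working it through.** **1. Look-back under the stated schedule.** The inputs are the days in D.3, Phase 2. Pairing Day 10 with Day 40 and Day 14 with Day 44 gives 10-day and 14-day regimens.

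Shortest look-back = assessment day − last treatment day. Longest look-back = assessment day − start of treatment (Day 0).

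| Regimen length | Assessment | Shortest | Longest |
|---|---|---|---|
| 10 days | Day 40 | 40 − 10 = 30 days | 40 − 0 = 40 days |
| 14 days | Day 44 | 44 − 14 = 30 days | 44 − 0 = 44 days |

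If the first dose is counted as Day 1, the longest values are 39 and 43 days.

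**2. Look-back with a record at the Day 10/14 stool collection.** 10-day regimens: 0 to 10 days. 14-day regimens: 0 to 14 days. The shorter interval still involves some looking back.

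**3. The plan's own sample size, used below.** The plan gives 46 per arm, from a prevalence of 86.4%, 95% confidence and 10% sampling error. The formula n = z² × p × (1 − p) / d² gives 1.96² × 0.864 × 0.136 / 0.10² = 45.14, rounded up to 46, and 5 × 46 = 230. The plan's figure reproduces. It is not based on any adverse-event rate.

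**4. Illustration of what under-reporting could do.** The plan gives no adverse-event rates and no reporting fraction, so everything here is assumed: true rates of 50% and 30% in two arms of 46, and the same fraction r of events reported in both. The observed rates are then r × 50% and r × 30%, and the observed difference is r × 20 points. Power is exact for the Pearson chi-squared test, two-sided 5%, one pair, no adjustment.

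| r | Observed rates | Difference | Power |
|---|---|---|---|
| 1.0 | 50% v 30% | 20 points | 49.0% |
| 0.9 | 45% v 27% | 18 points | 43.2% |
| 0.8 | 40% v 24% | 16 points | 37.8% |
| 0.7 | 35% v 21% | 14 points | 32.0% |
| 0.6 | 30% v 18% | 12 points | 26.6% |

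**5. Limits of the illustration.**

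- The reference row, r = 1.0, is perfect reporting. A Day 10/14 record would not reach that, so the gap between rows overstates the gain from the fix by an unknown amount.
- Equal r in both arms is an assumption. With r = 0.9 in the 50% arm and 0.6 in the 30% arm, the observed difference is 45% − 18% = 27 points, wider than the true 20. With the fractions reversed it is 30% − 27% = 3 points. Unequal reporting can therefore distort a comparison in either direction.
- Five arms give 5 × 4 / 2 = 10 pairs. At a Bonferroni level of 0.05 / 10 = 0.005, power is 19% with full reporting and 7% at r = 0.6.
- Even at r = 1.0 and no adjustment, power is below 50%. In this example the number of patients is a larger limit than reporting.

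**The case against.** The strongest reply is that the plan says when these data are recorded, not how they are obtained. A reader might infer that safety and adherence rest on a month's memory, and the text does not establish that. A patient diary handed in at Day 40/44 would fit the same sentence, and leftover tablets can be counted then as well as at Day 10/14. This stands: recall is an inference from silence.

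Relevant text may also lie elsewhere. Section D.4 says that "Further statistical analysis of H. pylori eradication efficacy, gut microbiota and immunological changes is described in Tasks section", and no such section is in the public document. Reference 28, a proposal for a standard side-effect score in H. pylori treatment studies, is listed but not cited in the body, which suggests that text on adverse events exists somewhere. This lowers confidence without removing the point. The pointer to the Tasks section concerns analysis of efficacy, microbiota and immunology, and a scoring instrument does not by itself change when it is applied.

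Three further replies have force.

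- The Abstract and Phase 2 both place safety at 1 month, so there is no contradiction to correct. This is a design choice that could be improved.
- Only clinical adverse events and adherence are affected. The microbiota and immunological parts of the safety objective come from stool and blood samples.
- The Day 10/14 stool collection need not be a clinic visit. If samples are taken at home, the fix needs a form with the kit or a call.

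A reader might also argue that poor adherence data would undermine a per-protocol efficacy analysis. The documents mention no such analysis, so that argument has no basis here.

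**Conclusion.** The point holds as a cheap improvement that should be made, with medium confidence. It is not an error in the plan. On the stated schedule, on-treatment adverse events and adherence are first recorded 30 to 40 days (10-day regimens) or 30 to 44 days (14-day regimens) after they occurred, while a sample collection at the end of treatment goes unused for this purpose. This risks under-reporting, mainly of mild events, in the clinical safety comparison between regimens. The conclusion assumes that no contemporaneous method, such as a diary, is described in text outside the public document.

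The interval is firm, because it follows from the plan's own days. The effect on the comparison is not quantified by the documents. The fall in power from 49% to 27% shows how such a loss could act under assumed rates and equal reporting. It should not be read as an estimate of the loss in this trial or of the gain from the fix.

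**What to change.** Add adherence and adverse-event recording at the existing Day 10/14 stool collection, by a short form returned with the sample, or by a call if there is no visit. State how each is obtained (for example diary or tablet count for adherence). Name this record as the main source for on-treatment clinical adverse events and adherence. Keep the 1-month and 12-month records for late events. If a diary or scoring form is already in use, it is enough to describe it in Phase 2 and say when it is completed.

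The cost is one short form or call for each of the 230 patients and a one-line amendment to the schedule. Treatment, the eradication assessments and the sample size are unchanged.
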